ED Staffing / Subject Accrual. Because it is not possible to staff the project continuously (168 hours/week), this study will use the following sampling frame that has been used successfully in our previous ED research to ensure obtaining a representative sample of Veterans presenting to the AAVA ED. Project staff in the ED will recruit patients for the study 5 days per week between the hours of 10AM to 6PM. The majority of the recruitment time will be spent in the ED between 10AM and 6PM because 65-70% of patients enter the ED during those hours. In addition, another three days/week will include a weighted sampling of recruiting between either 7AM-3PM or 3PM-11PM time period. Thus, a total of 8 shifts (8 hours each) will be staffed each week to recruit, consent, screen patients, conduct baseline assessments, and deliver brief advice. Based on our previous ED studies where we have used similar staffing schedules we expect to accrue the following numbers: 30 months of screening x ~130 patients/month approached = 3,900; it is expected that 80% (n=3,120) will agree to participate and will be screened. We conservatively expect that 15% of the screened patients will have a positive screen and will be randomized (450 randomized; 225 per group). Randomization Procedures. Stratified random assignment to conditions will be by sex and presence of an AUD (yes/no) defined as a score of 14 for men and 10 for women on the AUDIT. Randomization by sex will be used because men and women generally differ in their rates and nature of alcohol use, problems, and outcomes. Random assignment will also be stratified based on meeting criteria for past year AUD (yes/no) because of potential differences in problem severity and potential intervention response. Randomization will proceed in blocks of 10 within study cells, in order to equalize randomization over time. Follow-up staff will be blind to condition. Participants in both conditions will receive written information regarding alcohol and VHA resources and be re-contacted to complete 3-, 6-, and 12-months follow-ups.

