Using the VA criteria for hiring and training peers, we expect that there will be a range of mental health conditions that peer mentors have dealt with in their lives. We will not exclude peers because of any conditions for which they are in stable recovery. Our priority will be to hire Veterans who are in long-term recovery. Because the peer mentors will work as part of the research team and will be supervised by the PI and the research coordinator, with support from other clinician investigators, we will have close monitoring of peer staff, as well as other staff, and are prepared to address any mental health and substance use issues that arise. If a peer is experiencing relapse, they will be assisted in seeking needed care and will not work with participants until they are stable. Also, if a peer relapses, participants will be reassigned to an alternative peer (supervised via weekly group supervision and bi-monthly individual supervision).

Follow-up Methods and Assessments. At the 3-, 6- and 12-month post-randomization follow-ups, participants will be called to complete a telephone follow-up survey. Participants may have the option to meet in person if necessary. The TLFB interview during follow-ups will be audio recorded. At enrollment, study staff will obtain consent, telephone numbers, and addresses, as well as information for contacts, at least one of whom does not live with the participant, who should know their whereabouts in the next 12 months. In addition, the following procedures will be implemented: 1) reminder calls/ letters will be started one month prior to each follow-up assessment until completed; 2) incentives will be given to participants who complete follow-ups ; and 3) participants will be encouraged to call the study office with any questions, and to notify us of address/telephone changes. A review article contains more detailed information regarding the follow-up protocol that will be used.⁶¹ Using these strategies, we typically achieve 12-month follow-up rates exceeding 80% at each assessment point.^{49,62,63}

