Dissemination and Implementation Plan

Members of the research team are well-positioned to inform VHA policy on peer-delivered alcohol BIs, and follow-up linkage to care peer-delivered protocols to link VHA patients to primary and specialty care. We are acutely aware of VHAs priorities related to substance abuse and are well-positioned to rapidly disseminate key study findings. First, we will disseminate research findings through journal publication and presentations at conferences. We will submit at least three manuscripts to peer-reviewed journals geared toward health services researchers and/or clinicians working with Veterans who have alcohol and mental health problems and submit at least one presentation per year targeting researchers and clinicians. We will also seek out opportunities to utilize VHA cyber-seminars to reach VHA researchers and clinicians. Importantly, we will directly disseminate our findings to clinicians and policy leaders within the VHA (e.g., primary care and mental providers). Because the education of peer support specialists is important to the overall uptake of study results, investigators will keep leadership apprised of study findings and work to shape training efforts, with broader dissemination in mind. To increase the likelihood of broader use across the VHA, the proposed project will use an Effectiveness-Implementation Hybrid design⁴⁷ and employ qualitative methods to identify barriers and facilitators of implementation of the intervention and the linkage to care components nationally. If the peer-delivered intervention package is found to be effective, we plan to partner with VHA leadership to identify wider implementation strategies.

Project Management Plan

Timeline. The project will take place over four years (Table 3). The first six months will be used to hire and train staff and finalize protocols. In

Screening												
Follow-ups												
Informant interviews												
Data analysis												
Dissemination												

month 7, we will begin enrollment, with follow-ups ending in month 9, year 4. Key informant qualitative interviews will occur in the first 9 months of year 4. Dissemination of findings will begin with analyses of the screening data in month 10 of year one and continue through the end of the project.

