Resources: Facilities and equipment and key personnel roles. The majority of project personnel will be located at Center for Clinical Management and Research (CCMR; Drs. [name], [name], [name]) where office space and equipment for them will be provided. The ED at the VAAAHS will provide space for peer mentors and research supervisor, with a telephone, to conduct the research assessments and to conduct the brief personalized advice protocol. Key roles are described in the budget justification. Project staff in Ann Arbor will have weekly meetings to ensure that the study is progressing well. In addition, study staff will have a 2-hour meeting once a month to discuss logistical and larger scientific issues.

Data management and safety. [name] will be responsible for the safety and security of patient-level data, stored on firewall-protected servers at CCMR. A Master's-level data manager within CCMR will conduct the initial double data entry, cleaning, linkage and analysis. The project will create a shared study folder accessed by study personnel. Once the final file is completed in year four, in accordance with current regulations articulated by the 1996 Health Insurance Portability and Accountability Act (HIPAA) Privacy Rule, private health information will be stripped with the exception of ages and dates and kept physically separate on the VA secure network with password protection.

HUMAN SUBJECTS

Risks to Human Subjects

Human Subjects Involvement and Characteristics. Data will be collected from Veterans, men and women, ages 18 years and older, recruited from the VA Ann Arbor Healthcare System (VAAAHS) Emergency Department (ED). Screening will last through the end of month 12, year 3 (30 months). Follow-up assessments will begin at the start of month 10 in year 1 and continue until the end of month 12, year 4. Key informant qualitative interviews will occur in the first 9 months of year 4. Data entry, cleaning and/or analysis will begin at the start of month 7 in year 1 and continue through the end of year 4. Dissemination of findings and report writing will begin with analyses of the screening data around month 10 of year one and continue through the end of the project.

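### The plan gives two follow-up end dates three months apart, and the earlier one (month 9 of year 4) would cut off the 12-month TLFB for about 45 of 450 participants if it were applied

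*Combined protocol and SAP*

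**What the plan says.** Two sections of the combined protocol and SAP date the end of follow-up.

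- **Project Management Plan, Timeline.** The project lasts four years, with six months of set-up. Enrolment then starts in month 7, "with follow-ups ending in month 9, year 4". The prose gives no enrolment end date.
- **Human Subjects Involvement and Characteristics.** On enrolment: "Screening will last through the end of month 12, year 3 (30 months". On follow-up: "Follow-up assessments will begin at the start of month 10 in year 1 and continue until the end of month 12, year 4".

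Two other sections fix the quantities needed to choose between the dates.

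- **ED Staffing / Subject Accrual** builds the sample on "30 months of screening x ~130 patients/month approached = 3,900", ending at "450 randomized; 225 per group".
- **Follow-up Methods and Assessments** sets the visit schedule: "At the 3-, 6- and 12-month post-randomization follow-ups, participants will be called to complete a telephone follow-up survey".

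Under Data Analysis for Aim 1, the treatment effect is the between-arm difference in TLFB frequency averaged over the follow-up year, from a linear mixed model. The Missing data section says that model keeps participants whose follow-up is incomplete.

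**The concern.** Both dates stand in running prose as current plan, and they cannot both be right. The Timeline date also conflicts with the accrual plan that produces the sample size. A start in month 7 plus 30 months of screening ends in month 36, so someone randomized then is due a 12-month interview in month 48, three months after the Timeline closes follow-up.

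At stake is the 12-month TLFB for the last people enrolled. Aim 1 names 12 months as one of its three time points, and the mediation analysis uses 12 months as its later outcome. The power section allows for 20% attrition and makes no separate allowance for follow-up closed by the calendar. Planned power is only just above 80%, so a contrast at 12 months alone has little margin for a further loss.

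**Working it through.** **Inputs.** Enrolment starts in project month 7 (Timeline). Screening lasts 30 months (Subject Accrual; Human Subjects). Follow-up ends in month 9 of year 4, project month 36 + 9 = 45 (Timeline), or in month 12 of year 4, project month 48 (Human Subjects). The last visit is 12 months after randomization. The sample is 450, with 80% retained, giving 360 (Power and Sample Size Calculations). The documents give no month-by-month accrual, so I assume it is uniform: 450 / 30 = 15 per month.

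1. **Reproduce the plan's enrolment period.** Months 7 to 36 inclusive: 36 − 7 + 1 = 30 months. This matches the stated 30. Month 36 also follows from the Timeline's start month and the accrual section's 30 months, without using the Human Subjects dates.

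2. **Last enrolment month with a complete 12-month visit** = follow-up end − 12.
   - End of month 45: 45 − 12 = 33. Months 34 to 36 are uncovered: 3 × 15 = 45 participants, or 45 / 450 = 10%. Expected completers among them: 45 × 0.8 = 36.
   - End of month 48: 48 − 12 = 36. Nobody is uncovered.

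3. **Range.** If month 9 means the start of that month (end of month 44), four months are uncovered: 4 × 15 = 60. The accrual section's own factors give 3,120 × 15% = 468 rather than 450; at 468 / 30 = 15.6 per month the loss is 3 × 15.6 = 46.8. Enrolment weighted towards the end would raise these counts, and early enrolment would lower them.

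4. **Earlier visits.** A participant enrolled in month 36 has the 6-month visit by 36 + 6 = 42, before either end date. Only the 12-month assessment is at risk.

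5. **Effect on the time-averaged primary analysis.** Under compound symmetry with within-person correlation ρ, a participant with k visits contributes information proportional to k / (1 + (k − 1)ρ). Going from 3 visits to 2:
   - ρ = 0.3: 3/1.6 = 1.875 to 2/1.3 = 1.538, a loss of 17.9% per affected participant.
   - ρ = 0.5: 3/2 = 1.500 to 2/1.5 = 1.333, a loss of 11.1%.
   - ρ = 0.7: 3/2.4 = 1.250 to 2/1.7 = 1.176, a loss of 5.9%.

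   With 10% of participants affected, total information falls by about 1.8%, 1.1% and 0.6%. The detectable effect rises by at most 1/√(1 − 0.018) = 1.009, under 1%. The values of ρ are assumed; the documents give none.

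6. **Effect on a 12-month-only contrast.** Normal approximation, two-sided 0.05: power = Φ(d√(n/2) − 1.96), with n per arm.
   - Plan's figure first: n = 180, d = 0.30: Φ(2.846 − 1.960) = 81.2% (noncentral t: 81.0%), against the stated 80%.
   - After the loss: 360 − 36 = 324, so n = 162: Φ(2.700 − 1.960) = 77.0% (noncentral t: 76.8%).
   - The effect detectable with 80% power moves from about 0.295 to 0.311.

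   The power section attaches d = 0.30 to total AUDIT scores. I apply the same standardized effect to the TLFB.

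**The case against.** A reader might infer that 12-month outcomes for about 45 participants would never be collected. The documents do not support that. The Human Subjects section says follow-up will "continue until the end of month 12, year 4", which covers all 450, and nothing shows that staff would work to the Timeline date instead. The bars of the timeline table are missing from the text available, so the table cannot show which date was meant. The loss is therefore conditional.

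A reader might also take the fall from 81% to 77% as a loss of power for the primary analysis. It is not. The primary estimate averages over follow-up and keeps the affected participants' 3- and 6-month data. The plan examines change over time in a second model with an interaction, and names no 12-month-only test as primary. The fall describes only a contrast confined to that visit.

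Nor does a loss set by enrolment date imply bias between the arms. Randomization is in blocks of 10 within strata, so a calendar cut-off should fall about equally on both. The documents show a possible loss of precision and no more.

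Finally, the visit schedule is given consistently as 3, 6 and 12 months, so this could be called a slip in an administrative timeline. That is fair as to scale. But the date governs when data collection stops, and it cannot be met under the plan's own accrual period, so the contradiction stands.

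**Conclusion.** The two sections contradict each other on when follow-up ends, by three months, and only month 12 of year 4 fits the stated enrolment period and 12-month final assessment. That conclusion rests on the plan's own dates and needs no assumption.

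The size depends on which date is used: no loss under the Human Subjects date, and about 45 of 450 twelve-month TLFBs under the Timeline date. The 45 assumes uniform accrual and follow-up to the end of month 45. The cost to the primary time-averaged analysis would be small under the correlations assumed; the cost to an analysis of the 12-month visit alone would be about four points of power.

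There is a separate point on feasibility. Under the Human Subjects date the last interviews fall due at the end of month 48, when the four-year project also ends. Data entry, cleaning and analysis are planned to run alongside collection, and follow-up responses are entered in real time, which helps. No time is left, however, for late interviews, final cleaning and analysis after the last visit.

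**What to change.** In the Project Management Plan, Timeline, change the end of follow-up to month 12 of year 4, in line with Human Subjects Involvement and Characteristics, and check that the timeline table agrees. Add one sentence: every participant is followed to the 12-month assessment before the final analysis. The cost is one date and one sentence. The visit schedule, sample size and analysis model do not change.

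The lack of slack should be recorded as a separate planning matter, because its remedies are not free. Final analysis after month 48 would run beyond the four-year project. Closing enrolment after month 33 would leave 27 × 15 = 405 participants at the assumed rate, so the sample size and power would need restating. Neither step is needed to correct the date.
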